### 6.5.1.3.COVID-19

The incidence of the first occurrence of COVID-19 starting 14 days after the second, third dose, and BD of IP will be presented. COVID-19 is defined as symptomatic disease based on the criteria specified in [Section 3.2.2](#). Cases are defined as participants meeting clinical criteria based on both symptoms for COVID-19 and positive RT-PCR test results.

Surveillance for COVID-19 symptoms will be conducted every two weeks by either telephone calls or eDiary prompts (alternating). Subjects reporting COVID-19 symptoms, as defined in Section 7.3.2 of Protocol Amendment 4, will be arranged an illness visit to collect an NP swab.

For this endpoint, a COVID-19 case will be identified as a positive post-baseline RT-PCR test result, together with eligible symptoms as described below in [Table 2](#).

**Table 2. Derivation for COVID-19**

	COVID-19
Post-baseline PCR results	Positive, AND
Systemic symptoms	at least TWO of the following systemic symptoms : Fever ( $\geq 38^{\circ}\text{C}/\geq 100.4^{\circ}\text{F}$ ), chills, myalgia, headache, sore throat, new olfactory and taste disorder(s); OR
Respiratory symptoms	at least ONE of the following respiratory signs/symptoms: cough, shortness of breath or difficulty breathing, OR clinical or radiographical evidence of pneumonia.

The date of documented COVID-19 (case) will be the later date of ([2 systemic symptoms reported, or respiratory symptom reported] and, [date of positive PCR test]). Specifically, the date of documented COVID-19 will be the later date of the following two dates (date of

Confidential

positive PCR test, and the date of eligible symptom(s)), and the two dates should be within 14 days of each other. Specifically:

- Date of positive PCR test,
- Date of eligible symptom(s), defined as earliest of
  - Respiratory symptom: earliest date of an eligible respiratory symptom is reported OR
  - Systemic symptoms: earliest date of the second eligible systemic symptom is reported

For Part A, the time to the first occurrence of COVID-19 will be calculated as:

Time to the first occurrence of COVID-19 = Date of documented COVID-19 – Date of first study dose + 1.

For Part B, the time to the first documented SARS-CoV-2 infection will be calculated as:

Time to the first occurrence of COVID-19 = Date of documented COVID-19 – Date of BD + 1.

Cases will be counted starting 14 days after the second dose, third dose, and BD, e.g., date of documented COVID-19 - Date of the second/third dose/BD  $\geq$  14.

[Table 3](#) includes the days when a RT-PCR test is scheduled for each of the 2-dose and the 3-dose regimens with/without booster. For the analysis of this endpoint, RT-PCR results at scheduled pre-dose visits will not be considered in the derivation of COVID-19 cases.

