- Fever (temperature $\geq 38^{\circ}\text{C}$) or chills
- Cough
- Shortness of breath or difficulty breathing
- Fatigue
- Muscle or body aches
- Headache
- New loss of taste or smell
- Sore throat
- Congestion or runny nose
- Nausea or vomiting
- Diarrhea

Elicited through interaction with the (in person or phone) and/or clinical evaluation by investigator

- Clinical signs indicative of severe systemic illness, Respiratory Rates ≥ 30 per minute, Heart Rate ≥ 125 beats per minute, $\text{SpO}_2 \leq 93\%$ on room air at sea level or $\text{PaO}_2/\text{FIO}_2 < 300 \text{ mm Hg}$, OR
- Respiratory failure or Acute Respiratory Distress Syndrome (ARDS), (defined as needing high-flow oxygen, non-invasive or mechanical ventilation, or ECMO), evidence of shock (systolic blood pressure $< 90 \text{ mmHg}$, diastolic BP $< 60 \text{ mmHg}$ or requiring vasopressors), OR
- Significant acute renal, hepatic or neurologic dysfunction, OR
- Admission to an intensive care unit or death.

From Medically-Attended HCP Visit (site or external)

- Positive virologic result by RT-PCR for SARS-CoV-2 infection

PCR results on NP Swabs and Saliva

Abbreviations: BP = blood pressure; COVID-19 = coronavirus disease 2019; ECMO = extracorporeal membrane oxygenation; FIO₂ = fraction of inspired oxygen; HCP = healthcare practitioner; NP = nasopharyngeal; PaO₂ = partial pressure of oxygen; RT-PCR = reverse transcriptase polymerase chain reaction; SARS-CoV-2 = Severe Acute Respiratory Syndrome coronavirus 2; SpO₂ = oxygen saturation.

It is important to note that some of the symptoms of COVID-19 overlap with solicited systemic ARs that are expected after vaccination with mRNA-1273 (eg, myalgia, headache, fever, and chills). During the first 7 days after vaccination, when these solicited ARs are common, investigators should use their clinical judgment to decide if an NP swab should be collected. The collection of an NP swab prior to the Day 1 and Day 29 vaccinations (for unvaccinated SOT and

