#### **6.5.1.5. Secondary Case Definition of COVID-19**

The incidence of the first secondary COVID-19 starting 14 days after the second dose and after the third dose of IP. The secondary case definition of COVID-19 is defined as one of these following systemic symptoms:

- Fever (temperature  $\geq 38^{\circ}\text{C}$ ) or chills, cough, shortness of breath or difficulty breathing, fatigue, muscle aches or body aches, headache, new loss of taste or smell, sore throat, nasal congestion or rhinorrhea, nausea or vomiting or diarrhea AND
- A positive NP swab, nasal swab, or saliva sample (or respiratory sample, if hospitalized) for SARS-CoV-2 by RT-PCR.

For Part A, the time to the first occurrence of secondary COVID-19 will be calculated as:

The time to the first occurrence of secondary COVID-19 = Date of documented secondary COVID-19 – Date of first study dose + 1.

For Part B, the time to the first occurrence of secondary COVID-19 will be calculated as:

The time to the first occurrence of secondary COVID-19 = Date of documented secondary COVID-19 – Date of BD + 1.

Confidential

Cases will be counted starting 14 days after the second dose, third dose, and BD, e.g., date of documented secondary COVID-19 – Date of second/third dose/BD  $\geq$  14.

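### SAP 6.5.1.3 does not confine the symptom date to the period around the positive PCR, and SAP 6.5.1.5 sets no symptom-to-PCR interval or case date

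*SAP*

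**What the plan says.** SAP 6.5.1.3 states that "a COVID-19 case will be identified as a positive post-baseline RT-PCR test result, together with eligible symptoms as described below in" Table 2. Table 2 defines eligibility by type of symptom and by number (two systemic or one respiratory), not by timing. The symptom date is the earlier of two dates:

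- "Respiratory symptom: earliest date of an eligible respiratory symptom is reported OR"
- "Systemic symptoms: earliest date of the second eligible systemic symptom is reported"

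The case date is the later of the symptom date and the PCR date, "and the two dates should be within 14 days of each other". The post-dose rule, "Cases will be counted starting 14 days after the second dose, third dose, and BD, e.g., date of documented COVID-19" minus the dose date, applies to that case date and not to the symptom date. No start of the symptom search is given. Severe COVID-19 (6.5.1.4) is built on this derivation.

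SAP 6.5.1.5 reads: "The secondary case definition of COVID-19 is defined as one of these following systemic symptoms", together with a positive RT-PCR. It gives no interval between the two. It counts cases from a documented date that it does not derive.

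SAP 6.5.1.2 works from the test result: an infection is asymptomatic if there were no symptoms within 14 days of the positive result.

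Protocol 7.3.1 defines cases by samples taken within 72 hours of the symptom report. The SAP Introduction gives the SAP precedence where methods differ, and SAP Section 7 lists no changes from the protocol.

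**The concern.** In a study with up to a year of follow-up and symptom surveillance every two weeks, many participants will report a cough, headache or sore throat that has nothing to do with SARS-CoV-2. If the earliest such report fixes the symptom date, a later PCR-confirmed illness can fail the 14-day condition. The two systemic symptoms also need not belong to the same illness, so an old symptom can complete a new one.

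In the secondary definition, an unrelated symptom at any distance can be joined to a positive swab taken without symptoms.

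At stake are the counts and incidence rates of COVID-19, severe COVID-19 and secondary-definition COVID-19, and whether the infection categories fit together. Two programmers following the same text could produce different tables.

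**Working it through.** The plan states no expected number of cases or misclassifications, so there is no figure to reproduce. The check applies the rules to example participants and then gauges the scale under stated assumptions.

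**Step 1: main definition.** As written, S = min(earliest respiratory report, report of the second distinct systemic symptom). It is a case if |PCR − S| ≤ 14, dated max(S, PCR). The comparison applies the same rule to symptoms within 14 days either side of the PCR only.

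| Reports | As written | Limited to ±14 days |
|---|---|---|
| Cough D60; cough D200; PCR+ D202 | S = 60, gap 202 − 60 = 142, not a case | S = 200, gap 2, case dated D202 |
| Headache D60; fever only D200; PCR+ D202 | S = 200 (fever is the second systemic symptom), gap 2, case dated D202 | One systemic symptom, not a case |
| Cough D200; PCR+ D202; nothing earlier | S = 200, gap 2, case dated D202 | Same |

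**Step 2: secondary definition.** Take headache on D100 and a symptom-free positive PCR on D200. Under 6.5.1.5 there is one listed symptom and one positive RT-PCR, so it is a secondary case. Under 6.5.1.2 the gap is 200 − 100 = 100 days, so it is also asymptomatic. Swabs without symptoms are planned: at scheduled visits such as Day 57 and Day 113, and after close contact (Protocol 7.1.6 and Schedule of Events).

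**Step 3: fit with SAP 6.5.1.1.** That section describes SARS-CoV-2 infection as COVID-19 and asymptomatic infection combined. The first participant in the table meets Table 1 by the positive RT-PCR. That participant is not COVID-19 (Step 1) and not asymptomatic (cough two days before the PCR), so the two components no longer make up the total.

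**Step 4: scale, with assumed illness rates.** Let unrelated respiratory reports occur at a constant rate λ per person-year from the first dose of the part, and let the positive PCR fall uniformly over the counting window in SAP 6.5.2. The chance of an earlier report more than 14 days before the PCR is the mean over days t of 1 − exp(−λ(t − 15)/365.25).

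| Assumed λ | Day 43–394 (2-dose, no booster) | BD-Day 15–181 |
|---|---|---|
| 0.25 | 12.8% | 5.5% |
| 0.5 | 23.6% | 10.5% |
| 1 | 40.5% | 19.6% |
| 2 | 61.9% | 34.3% |
| 3 | 73.9% | 45.4% |

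These apply only under the literal reading, and only if every such report enters the symptom data.

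**Step 5: solicited reactions, conditional.** Protocol 7.3.1 notes that "some of the symptoms of COVID-19 overlap with solicited systemic ARs that are expected after vaccination with mRNA-1273". If such reactions were used as symptom reports, then myalgia D30, headache D31, fever D200, sore throat D201 and PCR+ D202 give S = 31, a gap of 171 and no case. Limited to ±14 days, S = 201 and it is a case dated D202. Study P301 rates after any dose (Protocol 1.2.2) are headache 64.7%, myalgia 61.5% and chills 45.4%, which sum to 171.6%. The share with at least two of the three therefore lies between (171.6 − 100)/2 = 35.8% and 171.6/2 = 85.8%.

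**The case against.** The strongest reply is that 6.5.1.3 is a pairing rule: the 14-day sentence means that only symptoms near the PCR are candidates, and the earliest of those is taken. Section 6.5.1.2 works that way, and the mismatch in Step 3 suggests that this was the intention. The reading is reasonable, but the text places the 14-day condition after the date has been chosen and never restricts the choice. What stands is that this is an ambiguity whose literal reading misclassifies, not proof that the sponsor will program it so.

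Second, a reader might infer from 6.5.1.5 that the documents contain no link at all between symptom and test. They do: Protocol 7.3.1 has the 72-hour rule, and with that rule applied the overlap in Step 2 disappears. But the SAP replaces 72 hours with 14 days in one definition, is silent in the other, claims precedence and reports no changes. Whether silence carries the 72 hours over is not stated. Nor does 6.5.1.5 turn an earlier symptom into a case by itself, since a positive RT-PCR is always required.

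Third, solicited reactions are collected as reactions in the 7-day eDiary, while COVID-19 symptoms come through notification, questionnaires, calls and illness visits. No section feeds the former into Table 2, though none excludes them. Step 5 therefore shows a possibility only.

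Finally, the endpoints are secondary in Part A and exploratory in Part B, with no between-group comparisons planned. That is correct and limits the consequence.

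**Conclusion.** The point holds as a defect of specification. Followed literally, 6.5.1.3 can both drop and create COVID-19 cases, and severe COVID-19 follows. Section 6.5.1.5 lacks an interval and a case date and can overlap with asymptomatic infection.

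A reader might go further and infer that COVID-19 will be undercounted by a known fraction. The documents do not support that. The main-definition error runs both ways, so its net direction is not established. The percentages in Step 4 rest on illness rates that the documents do not give and on the literal reading. The P301 range in Step 5 comes from a trial that excluded immunocompromised people and applies only if reactions are used as symptoms.

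A dropped case still counts as SARS-CoV-2 infection through its positive RT-PCR. No sample size, error rate or primary endpoint is affected. The change should be made because the written rule gives wrong classifications in plausible histories and the remedy is nearly free.

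**What to change.** Before database lock, amend the SAP as follows.

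- **6.5.1.3:** for each positive RT-PCR, consider only eligible symptoms reported within 14 days before or after the sample date. Take the earliest respiratory symptom, or the second systemic symptom, within that interval, with both systemic symptoms inside it.
- **6.5.1.5:** apply the same interval, and define the case date as the later of the symptom date and the PCR date.
- **Both sections:** state whether solicited reactions recorded from the day of injection through the following 6 days count as COVID-19 symptoms.
- **Reconciliation:** say how the 14 days relate to the 72 hours in Protocol 7.3.1, and record any departure in SAP Section 7.

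The cost is a few sentences and a small programming change. The interval is the one that SAP 6.5.1.2 already uses, and no extra data collection is needed.

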6. DELAYING OR DISCONTINUING STUDY TREATMENT AND PARTICIPANT WITHDRAWAL FROM THE STUDY

6.1. Criteria for Delay of Vaccine Administration

6.1.1. Individual Participant Criteria for Delay of Study Vaccination

Body temperature (oral) must be measured on dosing visits before vaccine administration. The following events constitute criteria for delay of injection, and if either of these events occur at the time scheduled for dosing, the participant may receive the study injection at a later date within the time window specified in the applicable SoE ([Section 10.1](#)), or the participant may be discontinued from dosing at the discretion of the investigator ([Section 6.2](#)):

- Acute moderate or severe infection with or without fever at the time of dosing
- Fever, defined as body temperature $\geq 38.0^{\circ}\text{C}/\geq 100.4^{\circ}\text{F}$ at the time of dosing (oral temperature preferred)

Participants with a minor illness without fever, as assessed by the investigator, can be vaccinated. Participants with a fever of $\geq 38.0^{\circ}\text{C}/\geq 100.4^{\circ}\text{F}$ will be contacted within the time window acceptable for participation and re-evaluated for eligibility. If the investigator determines that the participant's health on the day of dosing temporarily precludes injection, the visit should be rescheduled within the allowed interval for that visit if possible or at a time the participant is clinically stable according to the judgement of the investigator.

If a participant takes a prohibited drug therapy, an injection could be delayed within the visit window based on the joint decision of the investigator and the CRO's medical monitor ([Section 5.5.3](#)).

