healthy participants receiving 2 doses [Group A1 and Group A5]); prior to Day 1, Day 29, and Day 85 vaccinations (for unvaccinated SOT recipients of 3 doses [Group A2]); prior to Day 1 vaccination (for previously vaccinated SOT recipients [Group A3]), and prior to BD-D1 (for participants who receive a BD in Part B) can help ensure that cases of COVID-19 are not overlooked. Any study participant who reports respiratory symptoms during the 7-day period after vaccination should be evaluated for COVID-19.

During the course of the study, participants with symptoms of COVID-19 will be asked to return within 72 hours or as soon as possible to the study site to collect an NP swab sample (for RT-PCR) for evaluation of COVID-19 and collect a blood sample for immunologic assessment of SARS-CoV-2 infection. Both study site visits and telemedicine visits are referred to as illness visits ([Section 7.1.6](#)). The NP swab sample will also be tested for the presence of other respiratory infections. Additionally, a convalescent visit will be scheduled approximately 28 days (+7 days) after diagnosis ([Section 7.3.2](#)). At this visit, an NP swab sampling for viral PCR and a blood sample will be collected for potential immunologic assessment of SARS-CoV-2 infection. In addition, the study site may collect an additional respiratory sample for SARS-CoV-2 testing to be able to render appropriate medical care for the study participant as determined by local standards of care.

Cases are defined as participants meeting clinical criteria based both on symptoms for COVID-19 and on RT-PCR detection of SARS-CoV-2 from samples collected within 72 hours of the study participant reporting symptoms meeting the definition of COVID-19. Participants who are hospitalized for COVID-19 without the opportunity for a clinic visit will also be considered cases, assuming that the symptomology criteria for COVID-19 are met and a respiratory sample is positive for SARS-CoV-2 by PCR at a clinical laboratory improvement amendments certified laboratory. Investigators are encouraged to try to obtain a respiratory sample during the course of hospitalization for submission to the study central laboratory, if feasible. The investigator should determine if the criteria for severe COVID-19 have been met.

Severe COVID-19 is defined in [Section 7.3](#).

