### 6.5.1.2. Asymptomatic SARS-CoV-2 Infection

This is a secondary endpoint for Part A and exploratory endpoint for Part B. It is defined in participants with negative SARS-CoV-2 at baseline. Asymptomatic SARS-CoV-2 infection is identified by both the absence of symptoms and the presence of infection as detected by RT-PCR or serology tests. Specifically:

- Absent of COVID-19 symptoms within 14 days of positive virologic or serologic results
- AND at least one from below:
  - Positive serology test result based on bAb specific to SARS-CoV-2 nucleocapsid at scheduled visits, when blood samples for immunogenicity are collected, or
  - Positive RT-PCR test post-baseline (at scheduled or unscheduled/illness visits)

The date of documented asymptomatic SARS-CoV-2 infection is the earlier date of:

- Date of positive serology test result based on bAb specific to SARS-CoV-2 nucleocapsid, or
- Date of positive RT-PCR test post-baseline (at scheduled or unscheduled/illness visits), with absence of symptoms.

For Part A, the time to the documented asymptomatic SARS-CoV-2 infection will be calculated as:

Time to the asymptomatic SARS-CoV-2 infection = Date of asymptomatic SARS-CoV-2 infection – Date of first study dose + 1.

For Part B, the time to the documented asymptomatic SARS-CoV-2 infection will be calculated as:

Time to the asymptomatic SARS-CoV-2 infection = Date of asymptomatic SARS-CoV-2 infection – Date of BD + 1. Cases will be counted starting 14 days after the second dose and after the third dose, e.g., date of documented infection - Date of the second/third dose/BD  $\geq$  14.

Confidential

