### 6.5.2. Analysis of Infection Rates

For Part A and Part B, the number and percentage of subjects experiencing each of the infection events below will be summarized by participant group for the mITT Set:

- SARS-CoV-2 infection
- Asymptomatic SARS-CoV-2
- COVID-19
- Severe COVID-19
- Secondary case definition of COVID-19

For each of these summaries, the incidence rate (i.e. the infection rate) will be provided by participant group, calculated as the number of cases divided by the total person-time. The 95% CI of the incidence rate will be calculated using the exact method (Poisson distribution) and adjusted by person-time.

Person-time is defined as the total time from first dose of each part of the study (Part A or Part B) to the earliest of the following dates: date of event, dose date in next part, last date of study participation, censoring time, or efficacy data cutoff date.

For participants who are a case for symptomatic COVID-19, symptoms reported by these participants will be summarized.

For SARS-CoV-2 infection, asymptomatic SARS-CoV-2 infection, COVID-19, and severe COVID-19, the timeframe for the counting cases will begin at 14 days after the last planned dose and will differ by study arm:

- 2-dose unvaccinated without booster: from day 43 up to and including day 394,
- 3-dose unvaccinated without booster: from day 99 up to and including day 450,
- 3-dose previously vaccinated with Moderna COVID-19 vaccine without booster: from day 15 up to and including day 365.
- 2-dose unvaccinated with booster: from BD-Day 1 + 14 up to and including BD-Day 181.

Confidential

- 3-dose unvaccinated with booster: from BD-Day 1 + 14 up to and including BD-Day 181)
- 3-dose previously vaccinated with Moderna COVID-19 vaccine with booster: from BD-Day 1+ 14 up to and including BD-Day 181 .
- 3-dose previously vaccinated with mRNA or non-mRNA COVID-19 vaccine with booster: from BD-Day 1 + 14 up to and including BD-Day 181.

In addition, the COVID-19 and SARS-CoV-2 infection endpoints may be also analyzed by specimen types (i.e. NP swab, nasal swab, or saliva samples), calendar months, time periods, and all types of the diagnostic test (i.e., both RT-PCR results and other COVID-19 test results). The number and percentage of subjects experiencing COVID-19 may be summarized by specific variant groups. Listings of serum nAb and bAb levels against SARS-CoV-2, solicited ARs and unsolicited AEs will be provided for subjects infected by SARS-CoV-2.

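### Ignoring scheduled pre-dose RT-PCR results leaves a symptomatic participant whose only positive is the Day 85 swab, or the BD-D1 swab in Part A, as neither COVID-19 nor asymptomatic infection

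*SAP*

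**What the plan says.** **Case definition.** Protocol 7.3 and SAP 3.2.2 define COVID-19 as two listed systemic symptoms, or one respiratory sign or symptom, plus at least one RT-PCR-positive respiratory sample. Neither excludes a sample because of the visit at which it was taken.

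**SAP derivation.** SAP 6.5.1.3 adds, for this endpoint, that "RT-PCR results at scheduled pre-dose visits will not be considered in the derivation of COVID-19 cases". Severe COVID-19 (6.5.1.4) requires a 6.5.1.3 case. The positive PCR and the qualifying symptoms must lie within 14 days of each other.

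**Related endpoints.**
- Asymptomatic infection (6.5.1.2) accepts PCR positives from scheduled visits but requires the participant to be "Absent of COVID-19 symptoms within 14 days of positive virologic or serologic results".
- SARS-CoV-2 infection (6.5.1.1) is described as COVID-19 and asymptomatic infection combined. Its Table 1 counts a positive from either a scheduled or a symptom-prompted swab.
- The secondary case definition (6.5.1.5) needs one listed symptom and a positive sample, and states no pre-dose exclusion.

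**Counting start.** SAP 6.5.1.3: "Cases will be counted starting 14 days after the second dose, third dose, and BD". SAP 6.5.2: "the timeframe for the counting cases will begin at 14 days after the last planned dose", for example "3-dose unvaccinated without booster: from day 99 up to and including day 450".

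**Status of the rule.** SAP Section 1 says the SAP prevails over the protocol where methods differ. Section 7 lists no changes.

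**The concern.** Day 1 and Day 29 pre-dose swabs in the unvaccinated arms, and the Day 1 swab in Group A3, precede the start of counting in any case. The sentence can therefore change a result only at Day 85 (Group A2) and at BD-D1. Protocol 7.3.1 names both among the pre-dose swabs that "can help ensure that cases of COVID-19 are not overlooked".

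A symptomatic participant can reach such a visit. Protocol 6.1.1 says "Participants with a minor illness without fever, as assessed by the investigator, can be vaccinated", and one respiratory symptom is enough for the case definition. If the swab taken that day is the only positive, the SAP removes the participant from COVID-19 because of the swab and from asymptomatic infection because of the symptom.

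COVID-19 incidence is a Part A secondary objective. At stake are a possible undercount of COVID-19, a composite that does not equal its stated components, and a departure from the protocol case definition that no change section discloses.

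**Working it through.** **1. Reproduce the 6.5.2 window starts** (last planned dose day + 14):
- 2-dose unvaccinated: 29 + 14 = Day 43, as stated.
- 3-dose unvaccinated: 85 + 14 = Day 99, as stated.
- Previously vaccinated, dose 3: 1 + 14 = Day 15, as stated.

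**2. Days from the preceding dose to each pre-dose swab** (6.5.1.3 needs at least 14 after dose 2 or dose 3):
- Day 85, Group A2: 85 − 29 = 56. Inside.
- BD-D1, A2 to B2: 205 − 85 = 120. Inside.
- BD-D1, A3 to B3: 120 − 1 = 119. Inside.
- BD-D1, healthy adults: 149 − 29 = 120 on the protocol Table 10 day, or 129 − 29 = 100 on the day given in protocol 3.1.1. Inside on either.

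The day counts come from protocol Tables 8 to 10 and Section 3.1.1.

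**3. Apply the endpoint rules to Day 85, using the counting start in 6.5.1.1 to 6.5.1.3:**

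| Participant | COVID-19 | Asymptomatic | Infection by Table 1 | Infection as the combination | Secondary definition |
|---|---|---|---|---|---|
| Qualifying symptoms; pre-dose swab the only positive | no | no | yes | no | yes |
| Qualifying symptoms; illness-visit swab also positive within 14 days of them | yes | no | yes | yes | yes |
| No symptoms; pre-dose swab positive | no | yes | yes | yes | no |

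Only the first row fails. With the sentence removed, that participant becomes a COVID-19 case under 6.5.1.3 and the two readings of infection agree. The same trace holds for BD-D1 in the Part A analysis.

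**4. Apply the 6.5.2 windows instead.** Day 85 is before Day 99, so the event leaves COVID-19, asymptomatic infection and the composite alike, whatever happens to the sentence. The 6.5.2 window list does not name the secondary definition. For BD-D1 in Part A, Day 205 is after Day 99, Day 120 is after Day 15, and Day 149 (or 129) is after Day 43, so the mismatch remains.

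**5. Part A status of BD-D1.** SAP 5.2 keeps all Part A enrollees in the Part A sets whether or not they continue. SAP 6.1 runs the Part A period up to the booster, and 6.5.2 ends person-time at the next part's dose date. A pre-dose swab that day is the last Part A observation. SAP 6.5.2 lists only post-booster windows for boosted arms, so this step assumes that the Part A window starts also apply to those participants until the booster.

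**6. Part B status of BD-D1.** A positive swab makes pre-booster status positive (SAP 6.1), which removes the participant from the Part B mITT set (5.3.1, 6.5). Counting starts at BD-Day 1 + 14. The sentence has no effect there.

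**The case against.** **A second swab will usually rescue the case.** Protocol 7.3.1 calls for an illness visit with a swab within 72 hours for fever, chills, cough or breathlessness of any duration, and a positive there within 14 days of symptoms makes a COVID-19 case. This stands, and it makes the gap conditional. The rescue is not assured, however. Other symptoms prompt a visit only after 48 hours, while SAP Table 2 sets no duration. Swabbing in the 7 days after injection is left to judgment. The convalescent swab, about 28 days after diagnosis, will normally miss the 14-day link.

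**The event is not lost.** Correct: Table 1 and the secondary definition both capture it. The defect is inconsistent classification, not disappearance.

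**The protocol sentence on overlooked cases is not an endpoint rule.** Correct: it closes a paragraph on the overlap between COVID-19 symptoms and post-vaccination reactions. The departure rests on the case definition in protocol 7.3, not on that sentence.

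**The exclusion guards against counting reactogenicity.** The SAP gives no reason, but this would be a fair one. It justifies a condition on symptom onset, not discarding swabs from participants who were ill before the injection.

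**Day 85 is outside the 6.5.2 window anyway.** This also stands. It exposes a conflict between 6.5.1.3 and 6.5.2 that needs resolving, and it means that deleting the sentence would not be enough.

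**Conclusion.** The point holds in a conditional form. It needs qualifying symptoms and no other positive PCR within 14 days of them. Under the 6.5.1.3 counting rule it applies at Day 85 and at BD-D1 in Part A; under 6.5.2 only the Part A BD-D1 case remains, given the assumption in step 5 of the working. The departure from the protocol case definition is undeclared on either reading.

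The number affected is probably small and cannot be calculated, because the documents give no infection rate. Severe COVID-19 inherits the rule formally, although a severe case would be expected to yield another respiratory sample.

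A reader might infer three stronger things, none of which the documents support:
- **Every symptomatic positive at these visits is lost.** An illness-visit positive restores the case.
- **Post-booster incidence is biased.** A BD-D1 positive leaves the Part B analysis because of baseline status, not because of this sentence.
- **COVID-19 incidence is understated by a stated percentage.** Any such figure would be arbitrary.

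The endpoints are descriptive, with no formal hypothesis testing. This is a classification rule to correct before database lock, not a threat to the trial's main conclusions.

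**What to change.** 1. In SAP 6.5.1.3, limit the exclusion to swabs taken before counting starts: Day 1 and Day 29 in the unvaccinated arms, Day 1 in Group A3.
2. Count a later positive pre-dose swab (Day 85, or BD-D1 for Part A) as COVID-19 when qualifying symptoms began before that day's injection and within 14 days of the swab. Post-dose reactions are then not counted.
3. Reconcile the counting start in 6.5.1.3 (14 days after dose 2, dose 3 or booster) with that in 6.5.2 (14 days after the last planned dose), and state the Part A window for participants who are later boosted.
4. Align 6.5.1.1, Table 1 and 6.5.1.2 so that the composite equals its components. In particular, 6.5.1.2 should say how to classify a pre-dose positive whose symptoms begin only after the injection. Under step 2 that participant is not COVID-19, and under the present 6.5.1.2 wording is not asymptomatic either.
5. List any exclusion that is kept, with its reason, in Section 7.

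The cost is a text revision across four SAP subsections and Section 7, with matching changes to the derivation programs. It adds no visits or samples. The rule in step 2 needs symptom onset to be placed before or after the injection on the dosing day, so the sponsor should confirm that the recorded dates and times allow this.
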